#### 3.11 Sample size justification

Preliminary calculations, based on an estimated conservative change of 10% from baselines scores in QOL, as measured by the EQ-5D instrument total score (with a baseline of mean of 13 units and standard deviation of 5 units). We expect to detect a significant change with at least 80% power using 250 patients per treatment arm. To account for increased estimation variance due to propensity score-based reweighting (and a small rate of drop-out after enrollment), we plan to enroll 350 patients per treatment arm to ensure a reasonable expectation of significance.

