#### 3.4 Study Design

This is a pragmatic, quasi-experimental study wherein patients admitted for any of the aforementioned conditions will be allocated into treatment (ViSi mobile plus PROSPER) and control (PROSPER only) based on non-critical care bed availability on a floor unit. Specifically, for patients on colorectal service admitted to P10 floor, one side ("unit A") will be designated as an intervention arm while the other ("unit B") will serve as a control arm. For patients admitted to Hospitalist Medicine service; patients on " unit G21" will be designated as the intervention arm, and patients admitted to "unit G22" as the control arm. Our pseudorandomization scheme is based on the naturally occurring random variation in bed assignment by availability across both the intervention and control units on a given floor, or floors at the time of patient enrollment. Since bed designation is made by hospital admissions based on availability, it is independent of the care delivery processes across the study floors / units. Our approach is intended to reduce the

burden on frontline staff, i.e., changing existing workflows to randomize patients and track allocation in a database. It also serves to reinforce the embedded intent of our QI work. Participants, family members and clinicians will not be blinded to the intervention, and given our pragmatic design, we will not attempt to control patients' communication or information-seeking behaviors beyond the pseudo-randomization described above. The intervention wing will employ the following initiatives to improve the sleep quality, level of engagement, and overall care journey of patients.

1. Passive digital monitoring of vital signs – Blood pressure, heart rate, respiratory rate, oxygen saturation, and temperature – will be wirelessly and passively collected using a U.S. Food and Drug Administration-approved wireless technology, which is worn on the wrist and chest (ViSiMobile, Sotera, San Diego, Calif), and recorded data will be sent directly to the electronic medical record (Epic Systems Corporation, Verona,Wis) at protocolized set intervals. Abnormal vitals will trigger a nursing alert via text message or page. If an in-person assessment is warranted, handheld red-spectrum lighting will be used by nursing staff as an alternative to the standard overhead white lighting.

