#### 3.7 Patient Allocation to study groups

There is generally one patient per room and patient assignment to a room is largely driven by unit census (i.e., bed availability) as well as other clinical factors: e.g., need for an isolation room, nursing availability. All of these factors vary independently of the preferences of the patient or research team, reducing the risk for systematic bias. The unit of randomization is by pod on a floor. Research coordinators as part of the "on-boarding process" will also provide culturally competent instructions and in-person teaching for device use.

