#### 3.10 Statistical Analysis Plan

Means with standard deviations, frequencies and percentages will be used to convey descriptive statistics. Standard tests of association (chi-squared, t-tests) will be used for comparing characteristics between the control and intervention arm. Inverse probability weighting using propensity scores modeled from baseline covariates and instrumental variable analysis will be the quasi-experimental approach used to minimize any confounding bias from our pseudorandomization process. We will model most outcomes with weighted multivariate generalized mixed effects regression models, focusing primarily on estimate the average treatment effect. The effect of unit will be modeled using a random intercept term. Care utilization outcomes will be compared using standard time-to-event models and log-rank testing. Final analyses will be performed when all data has been entered, cleaned, and locked.

All analyses will be based on an intent-to-treat framework. For missing covariate values, a multiple imputation approach will be used. Outcomes will be assumed to be missing at random; a sensitivity analysis will be conducted to assess the robustness of significant findings to different magnitudes of missing data mechanisms.

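### The 80% power at 250 per arm holds for independent patients; it is not shown for the planned analysis, where four units fix the arm and unit is a random intercept

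*Combined protocol and SAP*

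**What the plan says.** - **Power (3.11).** The inputs are a 10% change from baseline in the EQ-5D total score, with baseline mean 13 and SD 5. The claim is "We expect to detect a significant change with at least 80% power using 250 patients per treatment arm". Enrolment is then raised to 350 per arm, and the reasons given are variance from propensity-score reweighting and a small drop-out. Section 3.9 makes EQ-5D at discharge the outcome on which the study is powered.
- **Allocation (3.4).** On the colorectal floor, unit A "will be designated as an intervention arm while the other", unit B, is the control. For the hospitalist service, unit G21 "will be designated as the intervention arm, and patients admitted to" unit G22 are controls. No unit contains both arms. The justification is "naturally occurring random variation in bed assignment by availability across both the intervention and control units".
- **Allocation (3.7).** "The unit of randomization is by pod on a floor". The number of pods is not given. Room assignment follows census "as well as other clinical factors: e.g., need for an isolation room, nursing availability".
- **Analysis (3.10).** "We will model most outcomes with weighted multivariate generalized mixed effects regression models", and "The effect of unit will be modeled using a random intercept term". No estimator, reference distribution or baseline EQ-5D covariate is named, and nothing says whether service enters the model.

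**The concern.** The plan states power for one analysis and describes another. When arm is constant within unit, a random intercept for unit adds the between-unit variance to the variance of the treatment contrast. More patients on the same units do not reduce that component. With two units per arm it is also estimated very poorly, so a Wald test can exceed its nominal error rate.

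At stake is whether the primary outcome has the power claimed, and whether a significant result could be credited to the device rather than to ordinary differences in care between units.

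**Working it through.** **Inputs from the documents.** Difference 0.10 × 13 = 1.3; SD 5; 250 or 350 per arm (3.11). Two units per arm (3.4). Random intercept for unit (3.10).

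**Assumed, not in the documents.** Two-sided 5% test. The 10% change is a between-arm difference with SD 5. The units have equal size (m = 125 or 175) and there is no weighting. ICC is 0, 0.005 or 0.01, which is a unit SD of 5√ICC = 0, 0.35 or 0.50 EQ-5D points. The four units of 3.4 are taken as the clusters.

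**Step 1: the plan's own figure.** For independent patients, SE = 5√(2/250) = 0.447 and 1.3/0.447 = 2.907. Power is 82.8% (normal) or 82.7% (t). Exactly 80% needs 233 (normal) or 234 (t) per arm. At 350 per arm, power is 93.0%. The stated 80% is therefore correct for independent patients.

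**Step 2: add the unit variance, treated as known.** With two units per arm, the variance of the difference is 25·ICC + 25(1 − ICC)/m.

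| ICC | Variance, 250 per arm | SE | Power | Variance, 350 per arm | SE | Power |
|---|---|---|---|---|---|---|
| 0 | 0.200 | 0.447 | 82.8% | 0.143 | 0.378 | 93.0% |
| 0.005 | 0.125 + 0.199 = 0.324 | 0.569 | 62.7% | 0.267 | 0.517 | 71.1% |
| 0.01 | 0.250 + 0.198 = 0.448 | 0.669 | 49.3% | 0.391 | 0.626 | 54.7% |

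For 80% power the variance may not exceed (1.3/2.8016)² = 0.2153. At 250 per arm, 0.200 + 24.8·ICC ≤ 0.2153 gives ICC ≤ 0.0006. At 350 the limit is about 0.0029. As m grows without limit, 25·ICC ≤ 0.2153 gives ICC ≤ 0.0086, so above that no number of patients on four units is enough.

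**Step 3: estimate the unit variance, as the planned model must.** This was simulated with the balanced closed-form REML fit, 1,000,000 trials per cell. SE² is the between-unit mean square over m when it exceeds the within-unit mean square, and otherwise the pooled mean square over m. The test is |difference/SE| > 1.96. The setting has no baseline adjustment and no service difference.

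| ICC | REML-Wald power, 250 | Type I error, 250 | REML-Wald power, 350 all effective | Type I error, 350 |
|---|---|---|---|---|
| 0 | 74% | 4% | 86% | 4% |
| 0.005 | 61% | 8% | 69% | 9% |
| 0.01 | 53% | 11% | 59% | 12% |

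Where type I error exceeds 5%, the power shown is flattered by it.

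**Step 4: how far unstated choices move the result.**
- *Estimator.* At 250 per arm and ICC 0, ML-Wald has 81% power. At ICC 0.005 it has 72%, with type I error 11%.
- *Baseline covariate.* With an assumed correlation of 0.5, the SD becomes 5√0.75 = 4.33, and REML-Wald at 250 and ICC 0 has 84.5%.
- *Reference distribution and service.* A between-unit t-test has 2 df if service is left out and 1 df if it is a fixed effect. At 250 and ICC 0, power is 37% and 18% respectively.
- *A real service difference left out of the model.* With an assumed 1-point difference between services, REML-Wald at 250 and ICC 0 falls to 37%, with type I error about 1%.

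**The case against.** The strongest defence is that the ICC may be close to zero. Beds are filled by availability, which should keep patient mix similar across paired units. At ICC 0 the claim can be met by ML-Wald at 250, by baseline-adjusted REML-Wald at 250 (assumed correlation 0.5), or by unadjusted REML-Wald if all 350 are effective. This stands: a reader might infer that the trial is underpowered, and the documents do not support that, because they give no ICC. The defence is incomplete, though. Section 3.7 adds isolation need and nursing availability to bed assignment, and balanced patient mix does not equalise nursing or care practice between units. Two units per arm cannot show how large such differences are.

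A second defence is that, if inference concerns only these four units, unit variance is not sampling error and the independent-patient figure stands. That is right, and the fix allows for it. But the plan specifies a random intercept and does not state that restriction. Nor can patient-level weighting remove a unit effect that is wholly nested in arm.

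Third, section 3.10 says the mixed model applies to most outcomes, not to EQ-5D by name. EQ-5D is the natural reading, because the only outcomes given a different method there are those for care utilization.

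Finally, one might read the simulated percentages as the trial's power. They are not. They assume units that differ only by arm and random variation, whereas 3.4 pairs them by service, and Step 4 shows how much that matters.

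**Conclusion.** The concern holds as a gap between the stated power and the planned analysis, not as an arithmetic error. The 80% at 250 per arm is right for independent patients and is not shown for a random-intercept model with two units per arm. The extra 100 per arm cannot be counted as an allowance for unit, since 3.11 assigns it elsewhere.

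The size depends on an ICC that the documents do not give. The most robust statement is the ceiling: under the Step 2 assumptions, 80% is out of reach above an ICC of about 0.0086, a unit SD of about 5√0.0086 = 0.46 points against a 1.3-point effect. The REML-Wald figures are illustrative and shift with estimator, reference distribution, baseline adjustment and the handling of service. Confidence is high in the gap and only moderate in any single percentage.

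**What to change.** In 3.11, state that the 80% assumes independent patients and no unit effect. Then choose one of two routes.

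- **(a) Conditional inference.** In 3.10, state that inference is conditional on these four units. Keep the independent-patient figure with that caveat, and state that a device effect cannot be separated from a unit effect.
- **(b) Random unit effect.** Keep the random intercept, include service in the model, and name the estimator, the reference distribution and whether baseline EQ-5D is a covariate. Replace the 80% with power and type I error under that model over a stated ICC range, for example 0 to 0.02.

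Under either route, state that the model applies to EQ-5D, and reconcile the pod of 3.7 with the units of 3.4.

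The cost is a short paragraph in 3.11 and a few sentences in 3.10, plus a simulation under (b). Either the scope of the conclusion (a) or the stated power (b) becomes less favourable. Enrolment and conduct do not change.

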#### 4.0 Sub-Study

This pilot sub-study is intended to compliment the parent trial by generating objective measures of sleep quality (sleep time, sleep latency, efficiency, awakenings after sleep onset) and leveraging additional patient-reported outcome measures (i.e. PROMIS) in this smaller population of consented patients. The present sub-study is nested within the parent trial, i.e. eligible patients for the parent trial will be eligible for the sub-study.

#### 4.1 Hypothesis

- a. Primary Hypothesis: Participants assigned to PROSPER with digital vital sign monitoring will trend toward improved objective sleep parameters compared to participants assigned to PROSPER without digital vital sign monitoring.
- b. Secondary Hypothesis: Participants assigned to PROSPER with digital vital sign monitoring will trend toward fewer sleep disturbances and reduced fatigue compared to participants assigned to PROSPER without digital vital sign monitoring.

#### 4.2 Objectives

- a. Primary Objective: Determine the preliminary effects of the PROmoting Sleep, Patient Engagement and Recovery (PROSPER) intervention with digital vital sign monitoring (experimental group) compared to PROSPER without digital vital sign monitoring (control group) on objective sleep parameters (total sleep time, sleep latency [minutes until sleep onset], sleep efficiency, frequency and duration of awakenings after sleep onset [WASO], and number of awakenings).
- b. Secondary Objective: Determine the preliminary effects of the PROSPER intervention with digital vital sign monitoring (experimental group) compared to PROSPER without digital vital sign monitoring (control group) on patient reported symptom outcomes (real-time fatigue, fatigue [PROMIS] and sleep disturbance [PROMIS]).

#### 4.3 Research Plan

- a. *Study Population:* In order to participate in the sub-study, participants must be enrolled in the PROSPER trial. We plan to enroll 100 participants from the parent trial in this pilot study, 50 participants from each arm of the parent trial. The inclusion and exclusion criteria for the sub-study are the same as the parent trial.
- b. *Inclusion criteria:* Adult patients (> 18 years of age), English-speaking and able to complete consent and survey materials are eligible to participate. Potential participants must be admitted to the hospital for an anticipated minimum of 3 nights.
- c. *Exclusion criteria:* Vulnerable populations (pregnant, incarcerated, history of delirium, suicidal ideation, ischemic stroke with measurable neurologic deficit, cerebral palsy, seizures), primary brain tumor/metastases patients) are not eligible. Patients concurrently enrolled in contact isolation with SARS-CoV2 will be excluded. Lastly, hospice or hospice-bound patients will also be excluded. Any patient can remove themselves from the study at any point.

#### 4.4 Study Methods

- a. Study design: The pilot sub-study will be integrated into the parent trial. This pilot study leverages a twogroup, pre-post test design to conduct preliminary tests for differences between the experimental arm (PROSPER intervention with digital vital sign monitoring) and the control arm (PROSPER intervention without digital vital sign monitoring) on objective sleep parameters and patient reported sleep disturbances and fatigue.
- b. Recruitment: Once participants are enrolled in the parent trial, they will be evaluated for inclusion in the pilot sub-study based on the availability of the device that measures objective sleep parameters (Actiwatch Spectrum Pro®). Thirty wrist actigraphy devices (Actiwatch Spectrum Pro®) are available for use at any given time. Fifty participants from the patient care units designated as the intervention arm for the parent trial will be enrolled as treatment patients in the substudy; fifty participants from the patient care units designated as the control arm will be enrolled as control patients in the substudy. Participants will be consecutively enrolled in the sub-study as they are enrolled in the parent study although enrollment may pause if wrist actigraphy devices are not available.
- c. Instrumentation: Objective sleep parameters will be assessed with the Actiwatch Spectrum Pro® during the course of hospitalization, consistent with the parent trial. Patient-reported sleep disturbances will be measured with the PROMIS Sleep Disturbance Adult Short Form. Patient-reported fatigue will be measured in real-time with a one-time global fatigue intensity rating over the course of the hospitalization and the PROMIS Fatigue Adult Short Form. The PROMIS instruments will be completed upon enrollment and discharge +/- 1 day, consistent with the parent trial.
- d. *Sleep:* The Actiwatch Spectrum Pro® (Phillips Respironics, Bend, OR) will be used to objectively assess sleep parameters. Sleep parameters will be computed using Actiware® software (V. 6.0). Data are stored in one-minute epochs. The software scores each epoch as wake or sleep. The software assigns rest, sleep, or active intervals based on activity counts. The default software settings will be used for the analysis as recommended by the manufacturer. Using an automated process, the software determines sleep start by searching for the first 10 minutes during which no more than one epoch is scored as "wake." The sleep parameters produced include total sleep time, sleep latency (minutes until sleep onset), sleep efficiency, frequency and duration of awakenings after sleep onset (WASO), and number of awakenings. Sleep variables will be scored for each 24-hour period, and averages over the course of hospitalization will be computed for nighttime sleep alone and nighttime sleep plus daytime naps. Wrist actigraphy is highly correlated with polysomnography, the gold standard for assessing sleep. Compared to polysomnography, wrist actigraphy is highly accurate (86%) and sensitive (96%) for detecting sleep. It has been successfully used to assess sleep and sleep disturbances across a wide range of populations, including people with cancer. Subjective sleep disturbances will be measured using the PROMIS Sleep Disturbance Adult Short Form described in detail below.
- e. *Fatigue:* Fatigue will be measured with a one-item fatigue intensity scale, using computerized ecological momentary assessment (real-time assessment) and the Fatigue Adult Short Form (PROMIS instrument). The Actiwatch Spectrum Pro® (Phillips Respironics, Bend, OR) contains a subjective event marker on the face of the activity monitor. This subjective event marker will be used as a real-time, single-item, global, self-report scale to measure real-time fatigue intensity. The fatigue intensity scores range from 0 (no fatigue) to 10 (worst). This rating of fatigue is particularly attractive for use in fatigued people due to ease of use and ability to capture repeated real-time measurements of fatigue throughout the day. While numeric intensity ratings do not provide information regarding the multidimensional nature of fatigue, this type of scale is suggested for use as a fatigue-screening device in clinical situations. A computerized ecological momentary assessment approach to collecting the real-time fatigue data was chosen to allow for improved documentation of compliance, avoid the problems with recall inaccuracies, and improve compliance. Data entered into the subjective event marker are stored in the onboard memory of the wrist actigraphy device.

We successfully used this computerized methodology with people with cancer, such as hematopoietic cell transplantation patients. Fatigue will also be measured using the PROMIS Fatigue Adult Short Form. The Adult Short Forms of the PROMIS instruments, including fatigue, are described together and in detail below.

f. Sleep Disturbance and Fatigue PROMIS Instruments: In concert with the NIH's move to utilize common data elements for research related to symptom science, PROMIS instruments will be used to assess patient-reported symptoms. We will use the Adult Short Forms for fatigue and sleep disturbances. These instruments are reliable, valid, and precise. Computerized versions will be used. The PROMIS instruments use a 5-point Likert scale and employ 7-day recall. Higher scores indicate higher levels of fatigue and sleep disturbances. Scores on all instruments are standardized (M = 50, SD = 10) and normed to a reference (U.S.) population; thus, enabling normative comparisons and providing an interpretative context for scores.

Table.	Variables	and	Measurement

Variable	Measure		
Fatigue	Patient-Reported Real-Time Assessments over course of hospitalization (Actiwatch		
	Spectrum Pro)		
	• 1-item fatigue intensity scale using the subjective event marker of the		
	Actiwatch Spectrum Pro		
	Patient-Reported Questionnaires		
	PROMIS Fatigue Adult Short Form		
Sleep	Patient-Reported Questionnaires		
Disturbances	PROMIS Sleep Disturbance Adult Short Form		
	Objective Real-Time Assessment averaged over the time of hospitalization		
	(Actiwatch Spectrum Pro)		
	Total Sleep Time		
	Sleep Latency (minutes until sleep onset)		
	Sleep Efficiency		
	
 
Frequency and Duration of Awakenings after sleep onset (WASO)
 
		
	Number of Awakenings		

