#### 3.5 Recruitment

Potential participants admitted to participating floors in the study will be identified in the EMR. Research coordinators will approach patients to participate in the study within 1-2 days of admission. The recruitment process will be documented and attested by the Investigators and their delegates.

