#### 4.4 Data Collection

Upon enrollment to the pilot sub-study, the wrist actigraph will be placed on the non-dominant wrist. The research staff will review real-time fatigue intensity rating procedures and instruct participants to leave the device in place for the duration of the hospitalization. Participants will be directed to carry on with normal activities. They will be asked to rate the intensity of fatigue at that moment in time on a 0 (no fatigue) to 10 (worst fatigue) scale five times during each day (upon awakening, 10:00 am, 2:00 pm, 6:00 pm, and at bedtime). An audible and vibratory alarm on the wrist actigraph will sound at preset times (10:00 am, 2:00 pm, and 6:00 pm) to remind participants to complete the real-time fatigue assessment. They will enter the rating directly into the subjective event marker of the wrist actigraph. Because of the expected time variability associated with awakening and going to bed, it will not be possible to program the Actiwatch Spectrum Pro® to alarm at these times. Participants will complete the PROMIS Sleep Disturbance and Fatigue questionnaires upon enrollment and hospital discharge +/- 1 day, in keeping with the parent trial data collection periods.

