#### a. Primary Objective

For each variable, differences between PROSPER with digital vital sign monitoring (the experimental group) and PROSPER without digital vital sign monitoring (the control group) will be calculated and reported with 95% twosided confidence intervals. Further exploratory analysis with ANCOVA models will incorporate covariates of baseline measures and length of stay to assess the relative efficiency gain of each covariate, as well as potential for confounding.

Based on previous work by the investigators, the confidence interval for the difference between groups should have expected lengths of no more than 54 (total sleep time, min), 12 (sleep latency, min), 5 (sleep efficiency, %), 17 (frequency and duration of awakenings after sleep onset, min), and 5 (number of awakenings).

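### The sub-study is labelled pre-post for objective sleep, but no pre-intervention actigraphy value is defined, and the main interval is an unadjusted comparison of groups formed by bed assignment

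*Combined protocol and SAP*

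**What the plan says.** The design statement in section 4.4 Study Methods (item a) reads: "This pilot study leverages a twogroup, pre-post test design to conduct preliminary tests for differences between the experimental arm". The same sentence extends the label to differences "on objective sleep parameters and patient reported sleep disturbances and fatigue". Objective sleep is the sub-study's primary objective (section 4.2).

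The timing of the measurements is as follows.

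- Section 3.5: "Research coordinators will approach patients to participate in the study within 1-2 days of admission".
- Section 4.4 Study Methods, item b: "Once participants are enrolled in the parent trial, they will be evaluated for inclusion in the pilot sub-study". The 50 patients per arm come from units already designated as intervention or control.
- Section 4.4 Data Collection: "Upon enrollment to the pilot sub-study, the wrist actigraph will be placed on the non-dominant wrist".
- Section 4.4 Study Methods, item d: "averages over the course of hospitalization will be computed for nighttime sleep alone and nighttime sleep plus daytime naps". The variables table agrees: "Objective Real-Time Assessment averaged over the time of hospitalization".
- PROMIS Sleep Disturbance and PROMIS Fatigue are completed at enrolment and around discharge, with a 7-day recall.

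Section 4.5a reports the difference between groups for each sleep variable with a two-sided 95% interval, then adds: "Further exploratory analysis with ANCOVA models will incorporate covariates of baseline measures and length of stay". Its stated aims are to judge each covariate's efficiency gain and the potential for confounding.

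**The concern.** A pre-post label on the primary outcome tells the reader that each patient's sleep before the intervention is known and can be used to separate existing differences from the device's effect. For the actigraphy variables the plan names no such value.

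This matters because allocation is not randomised. Section 3.4 calls the study quasi-experimental, and section 3.7 lists clinical factors such as isolation needs alongside bed availability. Two different services, colorectal surgery and hospitalist medicine, feed both arms. Sub-study entry also depends on a free actigraph, and no balancing by service is stated. The parent plan answers confounding with propensity weighting and instrumental variables (section 3.10). Section 4.5 mentions neither. If one arm has more surgical patients, or more patients who already slept badly, the difference goes straight into the headline interval.

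**Working it through.** **Step 1: which outcomes have a pre value.**

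| Outcome | First measurement | Summary | Pre value defined? |
|---|---|---|---|
| Actigraphy (5 variables) | From sub-study enrolment | Average over the stay | No |
| PROMIS Sleep Disturbance | Enrolment, 7-day recall | Enrolment and discharge | Yes |
| PROMIS Fatigue | Enrolment, 7-day recall | Enrolment and discharge | Yes |

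The pre-post label fits the PROMIS rows and does not fit the actigraphy row. Scoring by 24-hour period would yield a first-night value, but the plan does not designate it as baseline.

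**Step 2: the plan's own precision figures.** Section 4.5a gives maximum expected interval lengths of 54 min (total sleep time), 12 min (latency), 5% (efficiency), 17 min (awakenings after onset) and 5 (number of awakenings). They cannot be reproduced, because no SDs are given, but they can be inverted. For an unadjusted comparison with n = 50 per arm:

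L = 2 × t(0.975, 98 df) × SD × √(2/n), with t = 1.984 and √(2/50) = 0.20.

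For total sleep time, SD = 27 / (1.984 × 0.20) = 68.0 min. In the same way the implied SDs are 15.1 min (latency), 6.3 points (efficiency), 21.4 min (awakenings after onset) and 6.3 (number of awakenings).

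**Step 3: bias left in an unadjusted difference.** Let the arms differ systematically by d SDs on a pre-stay sleep measure that correlates ρ with the during-stay outcome. Then bias = d × ρ × SD. Both d and ρ are assumptions; the documents give neither. For total sleep time, in minutes:

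| d | ρ = 0.3 | ρ = 0.5 | ρ = 0.7 |
|---|---|---|---|
| 0.20 | 4.1 | 6.8 | 9.5 |
| 0.25 | 5.1 | 8.5 | 11.9 |
| 0.30 | 6.1 | 10.2 | 14.3 |

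The range is about 4 to 14 min. Against the half-width of 27 min this is 4.1/27 = 15% to 14.3/27 = 53%. The same shares apply to the other four variables, because bias and half-width both scale with the SD.

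**Step 4: possible gain in precision.** With a covariate of correlation ρ, the interval length becomes about L × √(1 − ρ²). From 54 min this gives 51.5, 46.8 and 38.6 min at ρ = 0.3, 0.5 and 0.7. The correlation of PROMIS scores with actigraphy is not given, so the gain from the covariates actually available is unknown.

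**The case against.** The best defence is that this is a pilot that estimates preliminary effects, already plans an ANCOVA, and names confounding as one reason for it. The term baseline measures can be read to include the enrolment PROMIS scores. That is a fair reading and it largely stands: the plan does not ignore confounding. It does not settle the point, because the adjusted model is exploratory, its covariates are not named, and service is not among them. The other covariate, length of stay, is no pre-treatment measure: the plan hypothesises that the intervention shortens it.

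Several stronger readings are tempting, and the documents do not support them.

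- *There is no sleep baseline at all.* This is not so. PROMIS Sleep Disturbance is taken at enrolment, and the parent trial's Table 2 lists the Richards-Campbell questionnaire at admission. What is missing is an objective baseline.
- *The analyst is forced to use the first worn night, which would cut the effect by 50–70%.* With an equal effect D on all nights and a slope b of 0.5–0.7, such a model would indeed return D − bD. But section 4.5a does not prescribe that covariate, and no actigraphy change score is planned.
- *Every worn night is on treatment.* The documents do not say whether the actigraph goes on before the monitoring device starts.
- *The bias is 14–20 min.* That is 0.2–0.3 × 68 and assumes ρ = 1.
- *Chance imbalance is unhandled.* At 50 per arm the standard error of the difference is 0.20 SD, so 0.2–0.3 SD is 1.0–1.5 standard errors. The interval already allows for this; only systematic imbalance is a bias.

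**Conclusion.** The point holds for the actigraphy variables. The design label is wrong for the sub-study's primary outcome, and the headline interval leaves systematic differences in service mix and prior sleep unadjusted although relevant covariates are already collected. For total sleep time the bias could be about 4 to 14 min against a 27-min half-width. That figure rests on the implied SD of 68 min and on assumed values of 0.2–0.3 SD for the imbalance and 0.3–0.7 for the correlation. The documents offer no evidence that an imbalance of this size exists. For an estimation pilot this is worth correcting and is not fatal to the sub-study.

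**What to change.** - In section 4.4 Study Methods, item a, describe actigraphy as a during-stay two-group comparison and keep the pre-post label for the PROMIS outcomes.
- In section 4.5a, take the main 95% interval for each sleep variable from a regression on arm that adjusts for service, enrolment PROMIS Sleep Disturbance and enrolment PROMIS Fatigue. Report the unadjusted difference beside it.
- In section 4.5a, name the baseline measures, and state that no worn night after the monitoring device starts is used as baseline.
- Say whether the parent trial's propensity weighting applies to the sub-study.

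The cost is a few sentences and one regression per sleep variable. No new visits, patients or questionnaires are needed. The adjustment will be only partial: the correlation of PROMIS with actigraphy is unknown, and because patients are approached 1–2 days after admission, the 7-day recall may include nights already spent on the unit. The report should say so.
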